8.3. Randomization and Blinding

Not applicable, study is open label and single arm.

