14.3.2.8	Summary of Subjects Reporting Treatment-Emergent Adverse Events (All Causalities) Leading to On-Study Death by MedDRA System Organ Class, Preferred Term, and Dose Level Ever Received	Safety
Safety: Laboratory Data		
14.3.3.1.1	Summary of Laboratory Values – Hematology	Safety
14.3.3.1.2	Shift Summary of Laboratory Values in Normal Ranges - Hematology	Safety
14.3.3.2.1	Summary of Laboratory Values – Serum Chemistry	Safety
14.3.3.2.2	Shift Summary of Laboratory Values in Normal Ranges – Serum Chemistry	Safety
14.3.3.3.1	Summary of Laboratory Values – Coagulation	Safety
14.3.3.3.2	Shift Summary of Laboratory Values in Normal Ranges – Coagulation	Safety
14.3.3.4.1	Summary of Laboratory Values – Urinalysis	Safety
14.3.3.4.2	Shift Summary of Laboratory Values in Normal Ranges – Urinalysis	Safety
14.3.3.5.1	Shift Summary of Laboratory Values in CTC Grade - To the Worst Abnormal Value (Tests with One Directional CTC Grade)	Safety

Table Number	Title	Population
14.3.3.5.2	Shift Summary of Laboratory Values in CTC Grade - To the Worst Abnormal Value (Tests with Two Directional CTC Grade)	Safety
14.3.3.6.1	Summary of Subjects with Treatment Emergent Thrombocytopenia of Grade 4 as Derived From Laboratory Data by Dose Level Ever Received	Safety
14.3.3.6.2	Summary of Subjects with Treatment Emergent Anemia of Grade 4 as Derived From Laboratory Data by Dose Level Ever Received	Safety
Safety: Vital Signs		
14.3.4.1	Summary of Systolic Blood Pressure	Safety
14.3.4.2	Summary of Diastolic Blood Pressure	Safety
14.3.4.3	Summary of Heart Rate	Safety
14.3.4.4	Summary of Respiratory Rate	Safety
14.3.4.5	Summary of Body Temperature	Safety

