MedDRA System Organ Class, Preferred Term, and Maximum Severity  
(Population: Safety Evaluable Subjects)

NOTE TO THE PROGRAMMER: shell will following the standard output.

- Reference: 16.2.7.2.1

PROTOCOL: INCB 18424-258  
 DRUG/INDICATION: Ruxolitinib/Myelofibrosis

(Page 1 of 1)  
 VERSION: First DMC-Draft

Table 14.3.2.2.2

Summary of Subjects Reporting Treatment-Emergent Adverse Events (All Causalities) by  
 MedDRA System Organ Class, Preferred Term, and Dose Level Ever Received  
 (Population: Safety Evaluable Subjects)

Variable	All Subjects (N=23)	CTCAE Grade				
		0 (N=2)	>5 10 (N=23)	>10 15 (N=14)	>15 20 (N=7)	>20 25 (N=1)
Number (%) of Subjects With Any TEAEs	10 ( 43.5)	1 ( 50.0)	3 ( 13.0)	5 ( 35.7)	1 ( 14.3)	0 ( 0.0)
Blood and lymphatic system disorders	1 ( 4.3)	0 ( 0.0)	0 ( 0.0)	1 ( 7.1)	0 ( 0.0)	0 ( 0.0)
Anaemia	1 ( 4.3)	0 ( 0.0)	0 ( 0.0)	1 ( 7.1)	0 ( 0.0)	0 ( 0.0)
Gastrointestinal disorders	6 ( 26.1)	0 ( 0.0)	0 ( 0.0)	4 ( 28.6)	2 ( 28.6)	0 ( 0.0)
Abdominal pain	2 ( 8.7)	0 ( 0.0)	1 ( 4.3)	1 ( 7.1)	0 ( 0.0)	0 ( 0.0)
Anorectal discomfort	1 ( 4.3)	0 ( 0.0)	0 ( 0.0)	1 ( 7.1)	0 ( 0.0)	0 ( 0.0)
Diarrhoea	3 ( 13.0)	0 ( 0.0)	0 ( 0.0)	2 ( 14.3)	1 ( 14.3)	0 ( 0.0)
Dry mouth	1 ( 4.3)	0 ( 0.0)	0 ( 0.0)	0 ( 0.0)	1 ( 14.3)	0 ( 0.0)
Haemorrhoidal haemorrhage	1 ( 4.3)	0 ( 0.0)	0 ( 0.0)	1 ( 7.1)	0 ( 0.0)	0 ( 0.0)
Nausea	1 ( 4.3)	0 ( 0.0)	0 ( 0.0)	1 ( 7.1)	0 ( 0.0)	0 ( 0.0)
. . . . .						
PROGRAM\OUTPUT: T_AESUM1.SAS\T_AE2.LST		DATE (TIME): 12DEC11(11:30)				

Note 1:TEAEs: AEs that began or worsened from baseline following the first administration of the study drug.  
 Note 2:N=the number of subjects who ever took a dose within the dose group, based on which the percent is calculated.  
 Note 3:For an AE that occurred for more than once to a subject, it is counted in the lowest dose when  
 the highest severity grade is recorded.  
 Reference: Listings 16.2.7.2.1

NOTE to the reviewer: numbers in the shell is from draft DMC output and is intended to show shell only.

PROTOCOL: INCB 18424-258  
DRUG/INDICATION: Ruxolitinib/Myelofibrosis

(Page 1 of 1)  
VERSION: First DMC-Draft

Table 14.3.2.3.1

Summary of Subjects Reporting Treatment-Emergent Adverse Events (All Causalities) by  
MedDRA Preferred Term (Sorted by Decreasing Frequency) and Maximal Severity  
(Population: Safety Evaluable Subjects)

NOTE TO THE PROGRAMMER: shell will following the standard output.

- Reference: 16.2.7.2.1

PROTOCOL: INCB 18424-258  

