14.3.3.1.2	Shift Summary of Laboratory Values in Normal Ranges - Hematology	Safety
14.3.3.2.1	Summary of Laboratory Values – Serum Chemistry	Safety
14.3.3.2.2	Shift Summary of Laboratory Values in Normal Ranges – Serum Chemistry	Safety
14.3.3.3.1	Summary of Laboratory Values – Coagulation	Safety
14.3.3.3.2	Shift Summary of Laboratory Values in Normal Ranges – Coagulation	Safety
14.3.3.4.1	Summary of Laboratory Values – Urinalysis	Safety
14.3.3.4.2	Shift Summary of Laboratory Values in Normal Ranges – Urinalysis	Safety
14.3.3.5.1	Shift Summary of Laboratory Values in CTC Grade - To the Worst Abnormal Value (Tests with One Directional CTC Grade)	Safety
14.3.3.5.2	Shift Summary of Laboratory Values in CTC Grade - To the Worst Abnormal Value (Tests with Two Directional CTC Grade)	Safety

PROTOCOL: INCB 18424-258  
 DRUG/INDICATION: Ruxolitinib/Myelofibrosis

(Page 1 of 1)  
 VERSION: Final

Table 14.3.3.6.1

Summary of Subjects with Treatment Emergent Thrombocytopenia of Grade 4 as Derived from Laboratory Data  
 by Last Dose Before Onset  
 (Population: Safety Evaluable Subjects)

MedDRA Preferred Term	All Subjects (N=xx)	Dose Level (mg) Subjects Ever Received					
		<=5	>5 10	>10 15	>15 20	>20 25	>25
		N=xx	N=xx	N=xx	N=xx	N=xx	N=xx
Number (%) of Subjects With Grade 4 Thrombocytopenia [1]	xx ( xx.x)	xx xx%	xx xx%	xx xx%	xx xx%	xx xx%	xx xx%

PROGRAM\OUTPUT: T\_xxxx.SAS\T\_xxxxx.LST

DATE (TIME) : DDMMYY (HH:MM)

Treatment-Emergent AEs: AEs that began or worsened from baseline following the first administration of study drug.

Note: Subjects are counted only once under in the lowest dose group.

Note: N=the number of subjects who ever took a dose within the dose group, based on which the percent is calculated.

Note: AEs that occurred following the date of treatment crossover were not included.

[1] Grade 4 Thrombocytopenia is defined as any occurrence of a treatment emergent hematology lab below 25 GI/L

Reference: Listing 16.2.8.1.4

PROTOCOL: INCB 18424-258  
DRUG/INDICATION: Ruxolitinib/Myelofibrosis

(Page 1 of 1)  
VERSION: Final

Table 14.3.3.6.2

Summary of Subjects with Treatment Emergent Anemia of Grade 4 as Derived from Laboratory Data  
by Last Dose Before Onset  
(Population: Safety Evaluable Subjects)

NOTE TO THE PROGRAMMER: similarly program this as Table 14.3.3.6.1, just need to update footnote about G4 anemia.

NOTE: the following vital sign tables will be programmed according to standard output.

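### The by-dose Grade 4 tables carry conflicting dose labels, and their lowest-dose footnote can credit a repeat-event subject's new onset to a lower dose column

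*SAP*

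**What the plan says.** **Labels.** SAP 10.1 lists Table 14.3.3.6.1 as "Summary of Subjects with Treatment Emergent Thrombocytopenia of Grade 4 as Derived From Laboratory Data by Dose Level Ever Received" and words the anemia table, 14.3.3.6.2, the same way. In Appendix B both shells are titled "by Last Dose Before Onset". The column header inside the 14.3.3.6.1 shell goes back to doses ever received.

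**Footnotes to the 14.3.3.6.1 shell**, which the anemia shell is told to follow:
- Counting rule: "Note: Subjects are counted only once under in the lowest dose group".
- Denominator: "N=the number of subjects who ever took a dose within the dose group, based on which the percent is calculated".
- Case definition: "Grade 4 Thrombocytopenia is defined as any occurrence of a treatment emergent hematology lab below 25 GI/L".
- Exclusion: "AEs that occurred following the date of treatment crossover were not included". Protocol 8.3 says of randomization and blinding: "Not applicable, study is open label and single arm".

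**Related rules.**
- SAP 5.9.3.4 defines the dose before an adverse event as the last non-zero dose before the event day. It does not say which event applies when a subject has several.
- SAP 5.2 groups certain adverse-event summaries by final titrated total daily dose, using the same six dose bands as this shell.
- The general adverse-event shells have their own tie-break. In Table 14.3.2.2.2 it begins "For an AE that occurred for more than once to a subject, it is counted in the lowest dose when" and goes on to name the occasion of the worst grade.
- SAP 8.1 makes new onset of Grade 4 thrombocytopenia, from laboratory data, the quantity to be summarized.

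**The concern.** The endpoint is the first Grade 4 value, and the shell title promises the dose that preceded onset. A rule that picks the lowest dose among several can overrule that promise. It would take a case away from the dose at which the count first collapsed and give it to the lower dose used after the hold. The table is the listed display of this endpoint by dose, in a trial whose secondary objective is a dosing strategy for patients with low platelets. A reader looking for a dose gradient would see it blunted or, in a small table, reversed. Because three labels in two places do not agree, two programmers could also produce different tables from the same specification.

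**Working it through.** The plan states no figure here, so there is nothing to reproduce. The check compares the rules and then follows subjects through them.

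**1. Lowest among what?** The word needs more than one candidate dose. The shell title points to doses before onset, and the case definition admits any value below 25 GI/L, so a subject can have several qualifying values. The sibling shells also break ties toward the lowest dose, within the occasions of worst grade. Here every qualifying value is Grade 4, so the sibling rule would give the same result: the lowest of the last doses before each Grade 4 value.

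**2. Direction.** Let d1 be the last non-zero dose before the first Grade 4 value, and d2, d3, … those before later ones. The footnote assigns min(d1, d2, …), which is at most d1. A subject can stay in the column of first onset or move down, never up.

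**3. Who can move.** Repeat values during one hold share the same last non-zero dose under SAP 5.9.3.4, so they move nobody. A move needs a restart in a lower column and a further Grade 4 value there. Protocol 8.6.3.1 provides for both steps: restart after a platelet hold is at 5 mg qd, and a second fall below 25 × 10⁹/L is foreseen.

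**4. Hypothetical subjects.** Paths are in mg/day; * marks a Grade 4 value on that dose. All start at 5 mg bid = 10 mg/day (Protocol 8.1).

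| Subject | Path | Column by footnote | Column by first onset |
|---|---|---|---|
| 1 | 10, 15, 20*, hold, 5* | ≤5 | >15 to 20 |
| 2 | 10, 15, 20*, hold, 5 | >15 to 20 | >15 to 20 |
| 3 | 10, 15, 20*, no restart | >15 to 20 | >15 to 20 |

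Counts in ≤5 and >15 to 20 are 1 and 2 by the footnote, 0 and 3 by first onset. With N based on doses ever taken, subjects 1 and 2 also enter the ≤5 denominator, although neither took that dose before first onset.

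**5. Effect on percentages, with assumed denominators.** Suppose 20 subjects ever took >15 to 20 mg, 8 ever took ≤5 mg, and 4 first onsets occurred at 20 mg/day. If r of the 4 have a repeat at 5 mg/day, the footnote gives (4 − r)/20 and r/8:

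| r | >15 to 20 mg | ≤5 mg |
|---|---|---|
| 0 | 4/20 = 20% | 0/8 = 0% |
| 1 | 3/20 = 15% | 1/8 = 12.5% |
| 2 | 2/20 = 10% | 2/8 = 25% |
| 4 | 0/20 = 0% | 4/8 = 50% |

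By first onset the figures stay at 20% and 0% throughout. This shows the mechanism only; it does not forecast this trial.

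**6. How many.** The documents give no repeat-event counts. Protocol 4.1.5 reports 8 of 50 subjects (8/50 = 16%) with a Grade 4 platelet count at the interim cut, so between 0 and 8 of those 50 could have moved. Protocol 4.1.4 describes Grade 3 or 4 thrombocytopenia in the placebo-controlled Phase 3 study as mostly a one-time finding, though in patients with higher platelet counts.

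**7. Anemia and hemorrhage.** Protocol 8.6.5 requires no dose change for anemia. The shift in Table 14.3.3.6.2 therefore needs a decrease made for another reason, such as the investigator discretion allowed in Protocol 8.6.2. The hemorrhage-by-dose tables, 14.3.2.3.3 and 14.3.2.3.4, have no shells of their own and are to be programmed like those shown. They inherit the lowest-dose-at-worst-grade rule, although new-onset Grade 2 or higher hemorrhage is also a named safety endpoint.

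**The case against.** The best defense is that the mismatch is only one of labels. In the sibling Table 14.3.2.1, whose figures are draft numbers shown for layout, doses ever received describe overlapping columns: the Ns are 2 + 23 + 14 + 7 + 1 = 47 for 23 subjects. The subjects with an event are still counted once: 1 + 3 + 5 + 1 + 0 = 10. On that view the header and N describe the columns, and the shell title governs the numerator. This is a fair reading and softens the title conflict, but nothing in the SAP states it, and it leaves the footnote open.

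It can also be said that the word onset already means first onset. But a subject has only one first-onset dose, and the footnote would then have nothing to choose between.

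A reader might go further and take the footnote to mean the lowest dose the subject ever received. Since everyone starts at 10 mg/day, no case could then appear above the >5 to 10 column, and four of the six columns would be empty by construction. The documents do not support this. The shell title and SAP 5.9.3.4 both tie the dose to the event, and the sibling layout figures place 5 + 1 + 0 = 6 of 10 subjects above >5 to 10 mg.

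The remaining objections stand in part. Few subjects may be affected, the split is descriptive, and restricting N is a preference. The crossover footnote excludes nobody in a single-arm study; it is leftover text.

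**Conclusion.** The point holds as a flaw in the table specification. The titles and header disagree, and the stated counting rule can place a subject with a repeat Grade 4 value below the column of first onset, against both the shell title and the new-onset endpoint. This rests on taking the footnote as the lowest of the last doses before each qualifying value, the reading that best fits the shell and its siblings.

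The number of subjects is unknown and probably small. For thrombocytopenia the shift follows from the protocol's hold and restart path; for anemia it depends on a dose decrease made for some other reason. A reader should not infer that the safety endpoint itself is compromised: the overall proportion and the life-table hazard do not use this dose assignment, and Listing 16.2.8.1.4 still shows the hematology data of these subjects. Even when corrected, the split remains descriptive, because titration is guided by platelet counts.

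**What to change.** 1. In both tables, replace the lowest-dose footnote with: *Each subject is counted once, at the last non-zero dose (SAP 5.9.3.4) before the first treatment-emergent Grade 4 value.*
2. Align the SAP 10.1 titles, the shell titles and the column header with this rule, and state that the final-titrated-dose grouping of SAP 5.2 does not apply to these two tables.
3. Delete the crossover footnote.
4. For hemorrhage Tables 14.3.2.3.3 and 14.3.2.3.4, either add the dose before first onset of Grade 2 or higher hemorrhage, or state that they do not show new onset by dose.
5. Optional: note beside N that it includes subjects who reached a dose group only after their first event, or restrict N to doses taken before first onset.

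The cost is edits to titles, header and footnotes and a small change to the numerator program (and to N if item 5 is taken up in full). No new data are needed. Subjects would still count in the N of several columns.
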